14.2.3. Scale design

14.2.3.1. Description

1. It will be based on a scale previously prepared (29). This will give support to the reference colorimetry and the cut points on which establish stages. The cut-off points, measured in concentrations (mg / dl), are considered as clinical relevance valued by a panel of experts(30,54).
2. The EDTA sample will be processed. Subsequently, 1 ml of the plasma of each sample is transferred to aliquots. The photograph of said aliquot will be made.
3. The absorbance of hemolysis will be analyzed. Six microliters of the plasma will be collected; because of the need for three repeated measurements.
4. The specific color of each sample (29) will be identified through the Photoshop software.

At least two design versions will be developed, based on visual colorimetry aspects.

It excludes jaundice for being healthy subjects, and try to reduce lipemia through strategically programmed blood extractions, as it appears in section 9.7.3.

In the first instance, the samples of the first period will be used for the design of the scale, and those of the second period for the validation process.

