2.14. Main and secondary variables

Main variable. Succeed peripheral vein catheter insertion at first attempt.

Secondary main variable. Visual intensity of hemolysis.

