14.2. Secondary principal analysis

14.2.1. Definition of variables

The main secondary variable is established:

Intensity of visual hemolysis. Discrete quantitative variable. It is measured in stadiums.

It aims to carry out the following secondary objective: Design and validate a visual scale of hemolysis.

To carry out its approach, through statistical methods, the following secondary variables are defined:

- o Absorbance of free hemoglobin in plasma. Continuous quantitative variable. It is measured in decimals.
- o Stadiums. Continuous quantitative variable. It is measured in absorbance ranges.
- o RGB colorimetry. Discrete quantitative variable. It is measured with whole numerical codes.
- o CMYK colorimetry. Continuous qualitative variable. It is measured in continuous percentage.
- o Blood samples. Discrete quantitative variable.
- o Observers Discrete quantitative variable.

The following variable is defined independently, since it will not be measured or used in the statistical analysis:

- Concentration of free hemoglobin in plasma. Continuous quantitative variable. It is measured in mg / dl.

However, it is considered an implicit variable in the scale on which the project is based (29) to carry out the modification of this and, therefore, the design of a new scale.

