The use of spectrophotometry is considered pertinent, although it is not the most discriminative technique currently used for the quantification of absorbances, if it is identified as discriminative and widely used for its price-quality ratio. In spite of having a sensitivity of 48% according to Shash JS et al., The rest of the precision values of this diagnostic technique are within the ranges considered acceptable (52). Their positive / negative likelihood ratios are unknown in order to extrapolate these results and, therefore, those that they expose would be distorted by the sample used in their research.

Shah JS et al. and other authors, in the last years of research in this field, affirm the relevance of the absorbance technique for the detection of hemolysis as greater precision than the concentrations, as it was done (51,52,53).

In addition, in the institution where the fieldwork is planned, it has access to said device and procedure, available and economically feasible, through a collaborating researcher of the present study.

The first samples obtained from the first volunteers included in this study will not be possible to subject them to visual inspection of the observers; it would still be in the design phase. However, these will be analyzed with spectrophotometry and photographed, so they would be measured equally but objectively.

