14.3. Secondary analysis attached

It has been considered that the approach of non-main secondary objectives could be carried out through the following methodology:

To identify the effectiveness of all the methods used in antebrachial venipuncture, in what refers to venipuncture at the first attempt.

It is intended to be addressed by means of a logistic regression, at the same time as the multivariate statistics for the main variable.

To evaluate the intensity of hemolysis of the blood samples, in what refers to the applied method, respectively.

It is considered that there is enough information on this subject to use a parametric test. In this case, the intensity of hemolysis is the dependent variable, it is considered justified to use an ANOVA test of a block test.

Identify the frequency of successful venipuncture at the first attempt and analyze if there is an association between it and the demographic characteristics of the individuals.

It is intended to be addressed through descriptive statistics. To analyze the association, a logistic regression will be performed; multivariate technique.

Analyze the correlation between methods used, intensity of hemolysis and pain.

It could be considered that enough information is known about pain to use parametric techniques, it is supposed to be the dependent variable and it is discrete. Therefore, it is intended to be approached using the ANOVA statistical technique or two-way F-test without interaction.

Identify and quantify adverse events, as well as their relation to skin types.

For the identification and quantification, a descriptive statistic will be carried out. In order to assess the possible association, using the Fitzpatrick scale, it is considered that there is not enough information about its distribution, so it is considered appropriate to use a nonparametric type test; the Kruskal-Wallis test.

14.4. Intermediate analysis.

Does not apply.

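### Section 14.3 does not say which haemolysis measure enters the blocked ANOVA; if it is the observers' visual stage, no period-1 scores are provided for and the within-subject comparison cannot be made

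*Combined protocol and SAP*

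**What the plan says.** - **Outcome.** Section 2.14 lists "Secondary main variable. Visual intensity of hemolysis", and section 14.2.1 repeats "Intensity of visual hemolysis. Discrete quantitative variable. It is measured in stadiums". Section 14.1.1 also defines it as visual and measured in stages. Section 14.2.1 separately lists stages as ranges of absorbance, and absorbance itself as a continuous variable.
- **Method comparison.** For haemolysis by method, section 14.3 takes the intensity of haemolysis as the dependent variable and says "it is considered justified to use an ANOVA test of a block test". It does not say whether intensity is the observers' stage, an absorbance-derived stage or absorbance, which sample is used, or what the block is.
- **Design.** Under sections 6.2 and 6.3 every subject receives one of three interventions and the comparator, one in each period, and serves as their own control.
- **Use of samples.** Section 14.2.3.1 says "the samples of the first period will be used for the design of the scale" and assigns the period-2 samples to validation. The sentence opens with a qualifier that makes the split provisional, but nothing says what comes after it.
- **Unscored samples.** Section 14.2.3.2 says: "The first samples obtained from the first volunteers included in this study will not be possible to subject them to visual inspection of the observers". The same paragraph adds that "these will be analyzed with spectrophotometry and photographed, so they would be measured equally but objectively".
- **Observer scoring.** Section 14.2.3.3.1, item E, has observers score only a chosen set of samples.
- **Sampling.** Table 3 (section 9.7.3) lists baseline, afternoon and evening samples for haemolysis analysis in both periods.

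**The concern.** The crossover was chosen so that each subject's intervention could be compared with the same subject's comparator. That needs an outcome measured in the same way in both periods. The outcome as defined is visual, and the visual scale is built from period 1 and validated on period 2. Under section 14.2.3.3.2, where the versions converge, the one with the higher concordance is used for hypothesis testing, so the final scale is not available until validation is done. No section returns to period 1 to have those samples staged by observers.

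If the ANOVA in section 14.3 is run on observer stage, the method effect can be estimated only between subjects within period 2. Leaving the variable unnamed also allows the choice between observer stage and absorbance to be made after the data have been seen.

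**Working it through.** **The plan's own figure.** The documents give no sample size or power for this ANOVA. The only haemolysis calculation (section 14.2.2) sizes the scale's positive prediction: reference 0.466, difference 0.334, two-sided alpha 5%. Reading the stated power of 1% as a beta of 1%:

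n = (1.960 + 2.326)² × 0.466 × 0.534 / 0.334² = 40.98, which rounds to the stated 41.

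That figure reproduces but does not bear on the method comparison.

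**Inputs.** There are six sequences (section 6.3). With 54 completers (sections 2.13 and 9.9) that is 9 per sequence; with 60 randomised (sections 6.3 and 14.1.2) it is 10. I take subject as the block, because section 6.2 makes each subject their own control. The within-subject correlation rho is not in the documents; I assume 0.3 to 0.7. Variances are in units of SD², with one value per subject per period.

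**Degrees of freedom for subject + period + method**

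| Data used | Subjects | Values | Comparator / each intervention | Model rank | Residual df |
|---|---|---|---|---|---|
| Both periods | 54 | 108 | 54 / 18 | 58 | 50 |
| Period 2 only | 54 | 54 | 27 / 9 | 54 | 0 |
| Both periods | 60 | 120 | 60 / 20 | 64 | 56 |
| Period 2 only | 60 | 60 | 30 / 10 | 60 | 0 |

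Using all three period-2 samples would not help. They all follow the same cannulation method, so method stays fully confounded with subject.

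**Variance of one intervention against the comparator, 54 completers**

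- Both periods, subject-blocked: 2(1 − rho)/18 = 0.111(1 − rho).
- Period 2 only, unblocked: 1/9 + 1/27 = 0.148.
- Ratio: 0.148 / [0.111(1 − rho)] = 1.333/(1 − rho).

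With 60 subjects the terms are 0.100(1 − rho) and 1/10 + 1/30 = 0.133, which give the same ratio.

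| Assumed rho | Variance ratio | SE ratio | Detectable difference, both periods | Detectable difference, period 2 only |
|---|---|---|---|---|
| 0.3 | 1.90 | 1.38 | 0.78 SD | 1.08 SD |
| 0.5 | 2.67 | 1.63 | 0.66 SD | 1.08 SD |
| 0.7 | 4.44 | 2.11 | 0.51 SD | 1.08 SD |

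Detectable differences are for 54 completers, 80% power, two-sided 5%, normal approximation: (1.960 + 0.842) × √variance. For example, 2.802 × √0.148 = 1.08.

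**The other reading.** If the dependent variable is absorbance, or a stage read off from absorbance ranges, the both-periods rows apply and there is no loss.

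**The case against.** A reader might infer that no period-1 sample gets a visual score and that the crossover is therefore lost as the plan is written. The documents do not go that far:

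- Section 14.2.3.2 rules out observer inspection only for the earliest samples from the first volunteers, and the period split in section 14.2.3.1 is provisional.
- Those samples still get absorbance and photographs, and section 14.2.1 defines stages by absorbance range, so a stage can be derived in both periods. Section 9.7.3 says haemolysis is evaluated by absorbance, and section 10.2.3 accepts visual inspection, absorbance or both.
- Section 14.3 does not name observer stage. Observer scores of a selected subset look more like validation data than an ANOVA outcome.
- The comparison sits among the non-main secondary objectives and no power is claimed for it. Separating development samples from validation samples is sound for building a scale.

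All of this stands, and it makes the loss conditional. It does not settle which variable is meant. The outcome is called visual in three places. Section 14.2.3.3.2 tests criterion validity by comparing absorbance with the observers' measures, which would be circular if visual intensity were simply derived from absorbance. And no section plans observer scores for any part of period 1.

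**Conclusion.** The point holds as a conditional one. Section 14.3 leaves the dependent variable open between a reading that keeps the crossover and one that loses it. On observer stage, with all of period 1 unscored and all of period 2 scored, the subject-blocked model cannot be fitted, and the fallback has 9 to 10 subjects per intervention with a standard error 1.38 to 2.11 times larger for the assumed rho. Because observers score only selected samples, the real numbers could be smaller, and some subjects might have no score. If some period-1 samples were scored after all, the loss would be smaller. On absorbance or an absorbance-derived stage there is no loss. It is worth fixing because a suitable paired measurement is already planned. The primary venipuncture analysis and the scale-validation hypothesis are not affected.

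**What to change.** In section 14.3, name the mean 414 nm absorbance of the baseline sample as the dependent variable for the comparison of methods, and fit a model with method, period and subject. The measurement is already planned in both periods. Section 14.2.3.1 provides for three readings per sample, and section 6.4 has haemolysis assessed by staff unaware of the method. The baseline sample suits the purpose: section 10.2.3 ties the clinical criterion to it, and it is drawn fasting (section 9.2), which limits interference from lipaemia.

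Report observer visual stage as supportive, for the samples actually scored. The comparison should not rely on scoring period-1 photographs later. Section 14.2.3.2 warns that colour does not carry over reliably between media, and photograph scores in period 1 beside plasma scores in period 2 would make the scoring medium coincide with period.

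The cost is SAP wording; no further sample or procedure is needed. The small downside is that the method result is expressed in absorbance rather than visual stages.

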14.2.3.2. Justification of the design of the scale

The scale or table of hemolysis for serum or plasma is used; proposed by MAYO Medical Laboratories (29) because it is the most used by other research studies and, the extrapolation of results is less difficult (64,65). Each cut point collects a color and is associated with a different concentration (29). It is considered necessary to clarify that the inference or association of colorimetry to concentrations in the new scale is not foreseen.

It is estimated that the use of these resources could be justified in the following cases:

It is considered relevant to start from this base scale (29) by the information it provides, in terms of colorimetry it is useful to decipher its coding, through the Photoshop software. It serves as a reference for the association of the information of colors that are found in the field work, and indirectly of its visual intensities of hemolysis. Thus, as of the points of cut that appear, to be able to establish stadiums.

It is foreseen the need to harmonize the structure of the support in which the photograph will be made, in this case in aliquots of the same capacity. Each clinical trial of bioequivalence requires different amounts of plasma, which is considered to alter the colorimetry of the photograph. In this way, possible fluctuations in capacities and quantities of biological material that could result in the case of the present protocol being carried out in different clinical trials due to the required sample size, would be avoided.

Although Photoshop is not the most accurate technique for measuring colors, difficulties have been encountered; because the correlation of colors in liquid and solid media does not adjust. In addition, the measurement of hemoglobin requires a fixed cut-off point of nanometers, so that the correlation of wavelength and its corresponding color would be biased and the information obtained would not be useful.

In addition, colorimetry is compromised in different liquid and solid media such as the computer screen format.

For the above reasons, the elaboration of versions in the design process of the new scale is considered justified. A priori it is not known if, the estimation of the colorimetry for the adjustment between the means, could cause biases or, on the contrary, it would not be significant enough. It has been considered that, in the validation stage, will reveal how much each of them fits.

The use of spectrophotometry is considered pertinent, although it is not the most discriminative technique currently used for the quantification of absorbances, if it is identified as discriminative and widely used for its price-quality ratio. In spite of having a sensitivity of 48% according to Shash JS et al., The rest of the precision values of this diagnostic technique are within the ranges considered acceptable (52). Their positive / negative likelihood ratios are unknown in order to extrapolate these results and, therefore, those that they expose would be distorted by the sample used in their research.

Shah JS et al. and other authors, in the last years of research in this field, affirm the relevance of the absorbance technique for the detection of hemolysis as greater precision than the concentrations, as it was done (51,52,53).

In addition, in the institution where the fieldwork is planned, it has access to said device and procedure, available and economically feasible, through a collaborating researcher of the present study.

The first samples obtained from the first volunteers included in this study will not be possible to subject them to visual inspection of the observers; it would still be in the design phase. However, these will be analyzed with spectrophotometry and photographed, so they would be measured equally but objectively.

14.2.3.3. Unidimensional scale validation

14.2.3.3.1. Precision analysis

A. RELIABILITY / REPRODUCIBILITY OF THE SCALE.

It reports the degree to which an instrument measures without error and whose variability of data is due to the real values that a variable takes, without being a product of bias or random error. It requires repetition of measurement of absorbances of the plasma of the subjects.

The instrument is calibrated and the hemolysis tubes will be harmonized, always being the same additive. The nurses have experience in the extraction of samples and the collaborator in the handling of the device correctly.

The variability between the samples will not be very large due to screening of inclusion and exclusion criteria of the clinical trial with drugs.

For all this, the systematic error decreases, although the total variance must be studied, with greater weight of said variance for the intraindividual variability (true differences and not due to biases or random).

B. INTERNAL CONSISTENCY.

A correlation could be made between absorbance ranges and stages to observe if both follow a linear association of increase.

C. DISCRIMINATING POWER.

It will not be evaluated from a statistical point of view. For the stages, what is studied in the literature as clinically relevant will be followed; it justifies that each stage discriminates objectively.

D. TEST-RETEST / INTRA-OBSERVER RELIABILITY.

The reproducibility of the instrument will be evaluated by evaluating the absorbance of the plasma of the blood samples in equivalent conditions, since time influences in which the conditions of the blood plasma change, repeating the measurement twice minimum. The technical error of measurement (ETM) can also be known by concordances (kappa index when apply) of measurements reported by observers. Same calculation will be carried out for all versions.

E. INTEROBSERVATORY RELIABILITY.

This item will be approached with the collaboration of several observers.

They will be provided with a training, and an independent CRR for blind evaluation, in which new versions will appear in different formats, and will ask them to score some blood samples, strategically selected. They will be required to score individually according to the stadiums. We will proceed to calculate the Kappa index for each stage and for each version.

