14.2.2. Statistical power and calculation of sample size

The choice of this secondary variable could be justified as the main one due to its statistical power, in relation to the sample size calculation, in order to conclude with a statistical

significance. That is, the sample size calculated for this variable could be included in the sample size calculated for the main variable; using the same fieldwork

According to a study (52) at a cutoff point for evaluation of free hemoglobin in plasma through absorbances and visual detection, the following is stated: of fifteen samples detected with absorbances, eight of them were not detected visually. That is, the visual inspection shows a predictive positive values (PPV) of 46.6%. It is tried to prove the veracity of this assumption and for it the following verification of hypothesis, of bilateral type is proposed:

H0: The positive prediction of intensity of hemolysis through visual stages is not optimal.

H1: The positive prediction of intensity of hemolysis through visual stages is optimal.

A calculation of GRANMO samples (63) has been carried out in the modality of proportions observed with respect to a reference. With an alpha error of 5% and a power of 1%, bilateral test. The reference proportion is 0.466 (52) and the objective is to reach a positive prediction of at least 0.80; It is considered optimal to detect the intensity of hemolysis in each stage. Therefore, the minimum difference to be detected is obtained through the objective of 0.80 - 0.466, that is, 0.334. Finally, it is obtained that at least 41 individuals are needed or, what is the same, 49 blood samples with a predicted proportion of losses of 20%; corresponds to possible samples with insufficient blood content for inspection.

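### Item C of the haemolysis-scale validation asserts from literature cut-offs alone that every stage discriminates, and no planned analysis tests adjacent stages or governs that assertion

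*Combined protocol and SAP*

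**What the plan says.** Designing and validating a visual haemolysis scale is a secondary objective (section 5.2.2), and visual intensity of haemolysis is the main secondary variable (sections 2.14 and 14.2.1).

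Section 14.2.3.3.1 lists the precision properties to be addressed. On discriminating power, item C says "It will not be evaluated from a statistical point of view", and gives as its ground that "what is studied in the literature as clinically relevant will be followed; it justifies that each stage discriminates objectively".

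On the cut-offs themselves:
- Section 14.2.3.1: "The cut-off points, measured in concentrations (mg / dl), are considered as clinical relevance valued by a panel of experts".
- Section 14.2.1, on concentration of free haemoglobin: it is defined separately "since it will not be measured or used in the statistical analysis".
- Section 14.2.3.2: "the inference or association of colorimetry to concentrations in the new scale is not foreseen".

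Other parts of the validation do use data. Item B is optional: "A correlation could be made between absorbance ranges and stages to observe if both follow a linear association of increase". Item E plans a kappa for each stage and each version of the scale. Section 14.2.3.3.2 plans concordance between observers and absorbance, with sensitivity, specificity and predictive values. Section 14.2.2 sizes a test of positive prediction.

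**The concern.** A clinically relevant cut-off says where a boundary ought to lie. It does not show that a person comparing plasma with a colour chart can place samples on the correct side of it. Item C moves from the first statement to the second with no trial data in between.

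The plan itself gives reasons to check. Section 14.2.3.2 concedes that colour rendering differs between liquid, solid and screen media and that the resulting bias is not known beforehand. Section 14.2.2 cites a study in which, "of fifteen samples detected with absorbances, eight of them were not detected visually". Item A of the precision analysis expects a narrow range: "The variability between the samples will not be very large due to screening of inclusion and exclusion criteria". A narrow range leaves less material for separating neighbouring stages.

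The stage is later used as an outcome. Section 14.3 compares haemolysis intensity between methods by ANOVA, and section 10.2.3 allows visual inspection to decide the haemolysis effectiveness criterion. If two adjacent stages are not separated, a one-stage difference between methods cannot safely be read as a difference in haemolysis.

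**Working it through.** **1. The plan's own figure for the scale.** The inputs, from section 14.2.2, are reference p0 = 0.466, target 0.80, difference d = 0.80 − 0.466 = 0.334 and two-sided alpha 5%. The stated power of 1% is read as a beta of 1%, that is, power 99%. With the null variance only:

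n = (z₀.₉₇₅ + z₀.₉₉)² × p0(1 − p0) / d² = (1.960 + 2.326)² × 0.466 × 0.534 / 0.334² = 40.98, so 41.

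Adding 20% gives 41 × 1.2 = 49.2, the stated 49. The figure reproduces. It is for one proportion against one reference value. The section describes the 0.80 target as optimal in each stage, but the sizing is done once, not per stage.

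**2. What success on that test would show.** Treat the 41 as single readings scored correct or not. The exact test then rejects at 26 or more correct (upper-tail probability 0.0226 at 0.466), which leaves 41 − 26 = 15 wrong. At the target itself, 33/41 = 0.805, which leaves 8 wrong. Nothing in a pooled proportion stops all 15, or all 8, from lying at one boundary. Success is therefore compatible with one pair of adjacent stages not being separated.

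**3. The other planned analyses, against item C.**
- *Kappa per stage and version (item E).* It measures agreement between observers. Observers who all place the samples of one stage in the neighbouring stage agree with each other and are all wrong.
- *Sensitivity, specificity and predictive values (section 14.2.3.3.2).* They are described for visual inspection in general, with no boundary named. If computed at a single cut, confusion between two stages on the same side of that cut leaves the two-by-two table unchanged.
- *Concordance with absorbance (same section).* It is used to choose between versions by the higher value. This is a relative rule with no level at which a stage fails.
- *Stage–absorbance correlation (item B).* It is optional. A linear rise over the whole range can coexist with two neighbouring stages that overlap.

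None of these entries refers to item C or states a result that would withdraw its conclusion.

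**4. From cut-off to stage.** The cut-offs are in mg/dl. Concentration is not measured, and colours will not be tied to it. Section 10.2.3 says that the absorbance corresponding to a cut-off is to be taken from the literature, and section 14.2.1 defines stages as absorbance ranges. The literature can therefore supply an absorbance boundary. The remaining step, from absorbance range to the stage an observer reads, is the one that needs trial data.

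**5. Data available for that step.** Section 14.2.3.1 assigns second-period samples to validation, and Table 3 takes three per subject in that period. With 54 completers that is up to 54 × 3 = 162 samples, or about 130 after the plan's 20% loss (162 × 0.80 = 129.6). Absorbance is measured three times per sample. Item E has observers score selected samples; the documents give neither the number scored nor the number of stages.

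**The case against.** The strongest reply is that item C is one sentence in a validation plan that otherwise relies on observers' readings. Poor stage separation would tend to lower kappa, concordance and positive prediction, and section 14.2.3.4 commits the work to STARD. This stands. A reader might infer that the plan forbids any statistical evaluation of the scale, or would declare it valid whatever the observers report. The documents do not support that; the refusal applies to item C only.

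Second, the word objectively may refer to how boundaries are set. Sections 9.7.3 and 14.2.3.2 use it of spectrophotometry, and absorbance ranges are distinct by construction. The text does not settle the meaning. On this reading the sentence is true but says nothing about a visual scale's discriminating power, so it still needs limiting.

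Third, the mismatch between mg/dl cut-offs and unmeasured concentration is not fatal, because absorbance equivalents are to come from the literature. This also stands, and it is why the gap is placed at the reading step.

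Fourth, the 8 of 15 missed samples do not show that this scale's stages fail. They concern visual detection at one cut-off in a cited study, and the plan uses the complement (7/15, its 0.466) as the value to beat. Likewise, a reader might infer from 49 samples and healthy volunteers that upper stages will be almost empty. The documents do not support a figure for that: 49 is a minimum, up to 162 second-period samples may exist, the scored samples are selected, and the number of stages is not stated.

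**Conclusion.** The point holds for item C. A listed validation property of the main secondary variable is concluded from literature alone, and no planned result at adjacent-stage boundaries could confirm or overturn it. Whether adjacent stages will in fact be poorly separated is unknown, and the documents do not allow a probability to be put on it.

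The size is modest. The stated 41 and 49 are unaffected, as are the primary endpoint and its analysis. What is at risk is the claim made for the scale and, through it, the reading of stage differences between methods. The conclusion assumes that the accuracy measures in section 14.2.3.3.2 are not already meant at every boundary, which the text does not say. If they are, the remaining defect is the unsupported sentence and its missing link to those results.

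**What to change.** 1. In section 14.2.3.3.1, item C, delete the clause after the semicolon in the sentence on literature cut-offs, or limit it to how the absorbance boundaries are set. Remove the statement that the property will not be evaluated statistically.
2. State in item C that discrimination is assessed from the sensitivity and specificity already planned in section 14.2.3.3.2, reported at each boundary between adjacent stages: observers' stage against absorbance, on the second-period validation samples.
3. Give 95% confidence intervals that allow for up to three samples per subject and several observers per sample, for example by resampling whole subjects.
4. Before the second-period readings, state the number of stages, the absorbance boundaries, how the scored samples are chosen and what result counts as support. The plan's 0.80 target is a natural starting point for that level.
5. Describe a stage as discriminating only where these results support it. Report sparse or unsupported stages as not evaluable, or merge them.

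The cost is a few lines of SAP text and a small analysis of absorbances and observer stages already being collected, with no extra blood or visits. The downside is that some stages may not be shown to discriminate, so the final scale may be coarser.
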